14.3 Analysis of Primary Endpoint

The primary hypotheses are that participants with chronic pain (PAIN) are more impulsive (larger k values) than participants without pain (NO PAIN) and that, within the same individual, k values will be larger in the naloxone-precipitated opioid withdrawal session compared to placebo. We will test these hypotheses using repeated measures analyses implemented in SAS PROC MIXED. The dependent variable is k (discounting). Independent variables include Group (PAIN vs. NO PAIN), a fixed, between-subjects effect and Condition (control vs. withdrawal), a repeated, within-subjects effect. The Group x Condition interaction will be examined to determine if group differences vary by condition. Planned contrasts will explore additive effects of chronic pain and withdrawal by examining whether discounting by the PAIN group in the withdrawal condition is greater than 1) discounting by the PAIN group in the control condition, or 2) discounting by the NO PAIN group in the withdrawal condition. To examine the effect of differing levels of peak aversive stimuli on discounting, we will conduct analyses using only data from the naloxone-precipitated withdrawal session that include peak COWS scores.

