| | The Group x Condition interaction will be examined to determine if | |
| | group differences vary by condition. Planned contrasts will explore | |
| | additive effects of chronic pain and withdrawal by examining whether | |
| | discounting by the PAIN group in the withdrawal condition is greater | |
| | than 1) discounting by the PAIN group in the control condition, or 2) | |
| | discounting by the NO PAIN group in the withdrawal condition. To | |
| | examine the effect of differing levels of peak aversive stimuli on | |
| | discounting, we will conduct analyses using only data from the | |
| | naloxone-precipitated withdrawal session that include peak COWS | |

Version #: 1.9 Version Date: 12/09/2020 Page 7 of 37

| | scores. |
|----------------------|---|
| Rationale for Number | Because there is no empirical data on within-subject changes in |
| of Subjects | discounting associated with naloxone precipitated withdrawal, we estimated change using data from a study by consortium PI [name] that used similar measures and found abstinence from smoking in nicotine-dependent individuals' decreased discounting rates ($f2$ =.02). For between group differences, we relied on data from our pilot study showing a correlation between pain and discounting (rho=.25) consistent with a small to medium effect size ($f2$ =.08). Three reported effect sizes for studies comparing opioid and tobacco dependent participants and non-dependent participants show much larger effects sizes (approximately $f2$ =0.4). Thus, basing the sample size on the effect size seen in the pilot study conservatively yields a sample size that will provide more than sufficient power to detect a group difference. Using these within-subject and between-subjects effect sizes, and assuming a correlation among repeated measures of 0.5, a final, analysis sample of 100 (50 per PAIN and NO PAIN groups) will provide greater than 80% power to detect significance (alpha=.05, 2-tailed) for between groups main effects, within-subject effects of condition, and the interaction between the two. |

Version #: 1.9 Version Date: 12/09/2020 Page 8 of 37

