9.4 Impulsivity Measures

9.4.1 Delay Discounting

Delay discounting is the relative preference for smaller sooner over larger later rewards, an aspect of impulsivity. Most individuals would prefer an immediate \$100 over \$100 delayed by 1 year. However, when faced with the choice between receiving \$95 now versus \$100 in 1 year, preferences for the delayed reward may increase. By assessing such choices across multiple delays, delay discounting quantifies the devaluation of rewards over time, which allows for an index of overall discounting rate (k). Delay discounting will be measured 30 minutes after IM injection during each session.

Version #: 1.9 Version Date: 12/09/2020 Page 17 of 37

9.4.2 Validated trait impulsivity measures.

Participants will also be assessed for trait impulsivity using four personality questionnaires assessing impulsivity or closely related constructs during screening. Scales will include the Barratt Impulsivity Scale-11 (85, 86); the Eysenck Impulsivity Questionnaire (87); the Sensation Seeking Scale (88); and the Zimbardo Time Perspective Inventory (89).

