9.5 Opioid Withdrawal Measures

These measures are very familiar to the PI ([name]) and utilize standard tools that will be collected by trained research staff. In each session, the opioid withdrawal measures will be collected at baseline and every 15 minutes following IM injection. They include the COWS (23, 107); Subjective Opiate Withdrawal Scale (SOWS) (24), and VAS ratings of subjective drug effects (108, 109).

The COWS is an 11-item rating system that is completed by a trained observer. Total scores range from 0 to 47, and withdrawal is classified as mild (5–12), moderate (13–24), moderately severe (25–36), or severe (>36).

The SOWS is a self-report instrument that asks participants to rate their level of current opioid withdrawal on 16 symptoms using a 5-point Likert scale (Not At All to Extremely). Answers to the 16 items are summed for a total score.

There are six VASs of subjective drug effects: high, drug effect, good effects, bad effects, liking, and sick. Each scale is a 100-point line anchored at one end with "not at all," and at the other with "extremely." The participant positions an arrow along the line using the keypad to indicate his or her answer of how s/he is feeling at that moment.

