14.2 Demographic and Baseline Characteristics

The PAIN and NO PAIN groups will be compared on all matching variables (methadone dose, cigarettes smoked per day, annual income, years of education, and age) using t-tests and chi-square tests as appropriate. If statistically significant differences are detected despite efforts to match during recruitment, matching variables will be included as covariates in subsequent analyses. It is recognized that this method is inferior to formal matching; therefore, substantial effort will be devoted to locating appropriately matched individuals. Measures obtained at 15-minute intervals during each session (pain, vital signs, opioid withdrawal, etc.) will be examined in terms of group comparability and to

Version #: 1.9 Version Date: 12/09/2020 Page 24 of 37

confirm that naloxone precipitated withdrawal symptoms compared to placebo. All psychometric, scaled measures will be scored according to standardized algorithms and internal consistency reliability examined. Given the design of the study, unit level missing data is not anticipated. Item level missing data will be minimized through supervised administration of measures. Missing data patterns will be examined and multiple imputation (SAS PROC MI) or other strategies employed as appropriate. Using methods developed by co-I [name], nonlinear regression will be used to calculate individual values of k, larger k values indicate greater discounting or more impulsiveness. K values are normalized using log transformation for parametric analysis (45).

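### The supporting withdrawal-severity analysis uses the naloxone session alone, so stable differences between people in discounting can pass for, or hide, an effect of severity

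*Combined protocol and SAP*

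**What the plan says.** Section 14.3 (Analysis of Primary Endpoint) first sets out the main model: PROC MIXED with Group between subjects and Condition repeated within subjects. Its withdrawal hypothesis is a paired one: "within the same individual, k values will be larger in the naloxone-precipitated opioid withdrawal session compared to placebo".

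The section then adds a severity analysis. The aim is "To examine the effect of differing levels of peak aversive stimuli on discounting", and the method is "we will conduct analyses using only data from the naloxone-precipitated withdrawal session that include peak COWS scores". The Primary Analysis Plan in the protocol synopsis has the same restriction ("naloxone-precipitated withdrawal session that include peak COWS"). Neither place gives the model form or says whether Group is included.

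The data for an own-control analysis are already planned. Section 9.4.1: "Delay discounting will be measured 30 minutes after IM injection during each session". Section 9.5: "In each session, the opioid withdrawal measures will be collected at baseline and every 15 minutes following IM injection". No k is scheduled before the injection, so the placebo session is the only own-control measure of discounting.

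The one covariate rule is in section 14.2: "matching variables will be included as covariates in subsequent analyses". It covers methadone dose, cigarettes per day, income, education and age, and applies only when the two groups differ significantly. A person's own level of discounting is not covered.

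**The concern.** The stated aim is about the effect of severity, but peak COWS is an outcome of the session and is not randomised. With one session per person, its coefficient compares people who had more withdrawal with people who had less. Anything stable that goes with both higher k and higher COWS will create an association with no severity effect behind it. If the two run in opposite directions, a real effect can be hidden.

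The plan's own content makes such links plausible. Section 3 expects higher k in the PAIN group in both sessions. Section 14.4 explores somatization, depression and anxiety as correlates of discounting. Section 2.1 lists body aches and dysphoric mood among withdrawal symptoms. At stake is how a significant or null severity result would be read. The crossover gives each person a placebo-session k that would remove the stable additive part of the problem, and this analysis leaves it out.

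**Working it through.** **Inputs from the documents.** Analysis sample N = 100 (50 per group), two-sided alpha 0.05, and "assuming a correlation among repeated measures of 0.5" (synopsis, Rationale for Number of Subjects). Effect sizes are f² = 0.02 within subjects and 0.08 between groups (section 14.6). No power is stated for the severity analysis.

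**Plan's own figure.** The synopsis claims more than 80% power for the main effects and the interaction. Noncentral F, df 1 and 98:
- within-subject and interaction: λ = f²·N·m/(1−ρ) = 0.02·100·2/0.5 = 8, power 79.97%;
- between-group: λ = f²·N·m/(1+(m−1)ρ) = 0.08·100·2/1.5 = 10.67, power 89.9%.

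This agrees with the plan to rounding. The same ρ = 0.5 means that half the variance of naloxone-session log k is a stable difference between people.

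**Input assumed.** r is the correlation between the stable part of discounting and peak COWS. The documents give no value, so a range is shown.

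**Model.** In each session log k = √ρ·T + √(1−ρ)·noise, with total variance 1. COWS = r·T + √(1−r²)·noise. There is no true severity effect.
- Naloxone-only slope on COWS = r·√ρ. At ρ = 0.5: 0.1·0.707 = 0.071; 0.2·0.707 = 0.141; 0.3·0.707 = 0.212 SD of log k per SD of COWS. The standard error is about 0.10.
- Change-score slope = r·√ρ − r·√ρ = 0.

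Rejection rates, 20,000 simulated trials per setting, ρ = 0.5:

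| r (assumed) | Naloxone only | Naloxone k adjusted for placebo k | Change in log k |
|---|---|---|---|
| 0 | 5% | 5% | 5% |
| 0.1 | 11% | 7% | 5% |
| 0.2 | 29% | 13% | 5% |
| 0.3 | 57% | 24% | 5% |

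If the link between T and COWS operates within groups, adding Group to the naloxone-only model leaves the rates essentially unchanged (11%, 28%, 56%). Adjusting for placebo k removes only part of the bias, because one session measures the stable part with error.

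**Masking.** With a true slope of 0.25 SD and r = −0.3, the expected naloxone-only slope is 0.25 − 0.3·0.707 = 0.038. Power is 7%, against 69% for the change score.

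**Precision.** The variance of the difference is 2(1−ρ), against 1 for a single session. Power for a true slope of 0.25 SD with r = 0:

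| ρ | Variance of difference | Naloxone only | Change in log k |
|---|---|---|---|
| 0.3 | 1.4 | 69% | 55% |
| 0.5 | 1.0 | 69% | 69% |
| 0.7 | 0.6 | 69% | 88% |

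**What the change score does not remove.** Suppose a trait correlates 0.3 with COWS and alters the response to naloxone by 0.2 or 0.3 SD (assumed), with no additive effect on k. At ρ = 0.5 and no severity effect, both analyses reject about 9% and 14% of the time.

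**The case against.** The strongest reply is that this is one follow-on sentence. Severity is not among the hypotheses or objectives in section 3 and carries no power claim. Both primary hypotheses are tested in a model that uses both sessions. Section 14 also says a detailed SAP, with any modifications, will be written before the final analysis. All of that stands, and it limits the weight of the point. A reader might infer that the primary withdrawal result is compromised; the documents do not support that.

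Second, the model form is not stated, and Group may well be in it. If confounding ran only through Group (f² = 0.08, and an assumed group difference in COWS of 0.3, 0.5 or 0.8 SD), the false-positive rate would be 7%, 10% or 17% without Group and 5% with it. So Group would deal with that route. It does not deal with differences between people within a group.

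Third, the 5% for the change score follows from giving the trait the same additive effect in both sessions. Section 3 hypothesises that catastrophizing modifies the effect of withdrawal, and section 14.4 tests Condition by PCS. A modifier of that kind does not cancel, as the last check shows. A reader might infer that the change score turns severity into a causal comparison. It does not, and a positive change-score result also needs caution.

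**Conclusion.** The point holds as a modest improvement to a supporting, unpowered analysis. As written, that analysis cannot separate an effect of severity from stable differences in discounting that track with COWS, and nothing else in the plan repairs this.

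The size rests on r, which is not in the documents. The false-positive rate is 5% at r = 0 and about 11% to 57% for r from 0.1 to 0.3, given ρ = 0.5, N = 100 and a purely additive stable trait. A reader might take 57% as the expected error rate, but it is only the top of an assumed range. The mechanism is certain; how large it is in this trial is not known.

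**What to change.** In the SAP, define the severity analysis as a regression of each participant's naloxone-minus-placebo difference in log k on naloxone-session peak COWS, with Group in the model. As a sensitivity analysis, use the naloxone-minus-placebo difference in peak COWS as the predictor. Report the naloxone-only relation between k and peak COWS as descriptive.

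State next to it that the change analysis removes only stable additive differences, that it remains observational because severity is not randomised, and that factors which modify the response to withdrawal, such as catastrophizing, are not removed.

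The cost is SAP wording, and no new data are needed. The statistical downside is lost precision if the between-session correlation turns out below 0.5, as in the ρ = 0.3 row above. Even there, the naloxone-only analysis would have false-positive rates of about 8%, 20% and 38% at r = 0.1, 0.2 and 0.3.

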14.4 Analysis of Secondary Endpoints

First, general linear model analyses (SAS PROC GLM) will be conducted to independently examine the impact of Condition and Pain Catastrophizing (PCS) on discounting rate (k). Then, a single GLM analysis will be conducted that includes Condition, PCS, and the Condition–by-PCS interaction. A significant interaction will indicate effect modification. We will also examine the effect of biological sex on discounting, opioid withdrawal, pain VAS, and pain catastrophizing. Based on prior research, we expect females to have higher PCS scores. We will also explore how the type of chronic pain (musculoskeletal, neuropathic, mixed/other) will effect discounting. We will also explore associations between somatization (SCL-90), depression (PHQ-9) and anxiety (GAD-7) and discounting. ng.

Safety and tolerability data will be summarized by study medication.

Adverse event rates will be coded by body system and MedDra classification term. Adverse events will be tabulated by study medication and will include the number of patients for whom the event occurred, the rate of occurrence, and the severity and relationship to study drug.

Version #: 1.9 Version Date: 12/09/2020 Page 25 of 37

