| TITLE | The Effect of Chronic Pain on Delay Discounting in Methadone Patients |
|-------------------------|---|
| SPONSOR | D. [name] MHS |
| FUNDING | NIDA |
| ORGANIZATION | |
| NUMBER OF SITES | 1 |
| RATIONALE | The epidemic of opioid overdose deaths continues to rise, killing more persons in 2017 than HIV/AIDS at the height of that epidemic. Medication assisted treatment, including methadone and buprenorphine, is the standard of care for the treatment of OUD. However, chronic pain can reduce treatment efficacy during medication assisted treatment and is associated with illicit substance relapse, dropout, and subsequent overdose. Mechanisms by which chronic pain may influence the impulsive decision making (e.g., drug relapse) in persons with OUD have not been well characterized. A better understanding is needed of decision-making in this population. Two factors that can influence decisions to use drugs are impulsivity and acute opioid withdrawal. This proposal will test how chronic pain is associated with increases in impulsive decision making in OUD, whether impulsive decision making is greater when undergoing opioid withdrawal, and how catastrophizing may modify the association between withdrawal and impulsive decision making in patients with chronic pain and OUD. An ideal population for this developmental research project is methadone-maintained patients, who show high treatment attendance rates and will therefore assure study efficiency and reliable completion. |
| STUDY DESIGN | This proposal is a randomized double-blind placebo-controlled Phase 1 clinical trial / human laboratory study to assess the effect of acute opioid withdrawal precipitated by 0.1 mg IM naloxone on delay discounting in patients on MMT with and without chronic pain. |
| PRIMARY OBJECTIVE | Determine the effect of aversive stressors on delay discounting in persons in methadone maintenance. |
| SECONDARY OBJECTIVES | Investigate the degree to which trait pain catastrophizing modifies the association between opioid withdrawal and delay discounting in the PAIN group. Examine the effect of biological sex on discounting, opioid withdrawal, pain VAS, and pain catastrophizing Examine the association between somatization, depressive symptoms, anxiety and discounting. We expect to enroll 130 participants on MMT, 65 in the chronic pain |

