3 STUDY OBJECTIVES

We hypothesize that the chronic pain group (PAIN) will show greater delay discounting (greater impulsivity) than the group without pain (NO PAIN) in both the control and opioid withdrawal sessions; and that discounting will be greater in the withdrawal session than control session for both groups, with the greatest discounting observed in the PAIN group while in withdrawal.

Version #: 1.9 Version Date: 12/09/2020 Page 11 of 37

We also hypothesize that across PAIN and NO PAIN groups, pain catastrophizing will independently modify the effect of precipitated opioid withdrawal on delay discounting, with higher levels of catastrophizing associated with a stronger association between withdrawal and delay discounting

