3.2 Secondary Objectives

Investigate the degree to which trait pain catastrophizing modifies the association between opioid withdrawal and delay discounting.

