5.2 Secondary Efficacy Endpoints

Secondary outcome variables will include measures of pain and opioid withdrawal, i.e.

- Pain Visual Analog Scale (VAS)
- Clinical Opiate Withdrawal Scale (COWS)
- Subjective Opiate Withdrawal Scale (SOWS)
- Vital Signs
- Pupil Diameter
- VAS Ratings of Subjective Drug Effects

In addition, personality questionnaires assessing impulsivity will be collected at screening and compared across groups, including

- Barratt Impulsivity Scale-11
- · Eysenck Impulsivity Questionnaire
- Sensation Seeking Scale
- Zimbardo Time Perspective Inventory

In addition, pain catastrophizing will be assessed and will be a main predictor variable in the linear regression models assessing effect modification in study Aim 2.

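### The Aim 2 moderation model names no within-participant error term, and the plan contradicts itself on whether Aim 2 covers the PAIN group only or both groups

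*Combined protocol and SAP*

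**What the plan says.** Every participant attends a placebo session and a naloxone session (Section 4.1), and discounting is measured in each (Section 9.4.1). The primary model in Section 14.3 is a repeated-measures PROC MIXED analysis with "Condition (control vs. withdrawal), a repeated, within-subjects effect". The synopsis sample-size rationale was derived "assuming a correlation among repeated measures of 0.5".

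Section 14.4 changes procedure for Aim 2: "general linear model analyses (SAS PROC GLM) will be conducted to independently examine the impact of Condition and Pain Catastrophizing (PCS) on discounting rate". A single model with Condition, PCS and Condition-by-PCS follows, and the decision rule is "A significant interaction will indicate effect modification". No participant effect, REPEATED statement, RANDOM statement or Group term is listed. Section 5.2 describes the same analysis this way: "pain catastrophizing will be assessed and will be a main predictor variable in the linear regression models assessing effect modification in study Aim 2".

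On the population for Aim 2:
- **Synopsis, Secondary Objectives:** the question is whether catastrophizing "modifies the association between opioid withdrawal and delay discounting in the PAIN group".
- **Section 3:** the hypothesis is that "across PAIN and NO PAIN groups, pain catastrophizing will independently modify the effect of precipitated opioid withdrawal on delay discounting".
- **Section 3.2:** "Investigate the degree to which trait pain catastrophizing modifies the association between opioid withdrawal and delay discounting", with no group named.
- **Section 2.1:** catastrophizing is said to moderate chronic pain as well as withdrawal.
- **Section 14.4:** no population is given.

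**The concern.** Two k values from one person are correlated, and the plan itself assumes 0.5. A general linear model with only the listed terms would treat 100 completers as 200 independent rows. That distorts the tests in opposite directions. The residual variance is too large for within-person contrasts (Condition and Condition-by-PCS), so those tests become too strict. It is too small for PCS, which takes one value per person (Section 9.6.2 has it measured in Session 1), so that test becomes too lenient. The interaction is the sole criterion for effect modification, so the main risk is a false conclusion of no moderation.

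The population conflict matters separately. PAIN only means about 50 completers and both groups means about 100, and the choice decides whether Group belongs in the model. If the groups are pooled without Group and Group-by-Condition, and catastrophizing differs by pain status, the group difference that Section 14.3 looks for can appear as moderation by PCS.

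**Working it through.** **Inputs from the plan.** Two sessions per person (m = 2), correlation ρ = 0.5, two-sided α = 0.05, N = 100 (50 per group), within-subject f2 = 0.02. Assumed here: session SD of 1 on the log k scale, PCS in SD units, and an Aim 2 interaction as large as the plan's within-subject effect. The plan states no effect size or power for Aim 2.

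**1. The plan's own figure.** For Condition and Group-by-Condition, λ = f2·N·m/(1−ρ) = 0.02·100·2/0.5 = 8. With (1, 98) df the power is 0.7997, so the stated figure of more than 80% is reproduced to rounding.

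**2. Matching moderation slope.** Regress the within-person difference on PCS. The difference has variance 2(1−ρ), so λ = N·b²/(2(1−ρ)). Setting this to 8 at N = 100 gives b² = 0.08, b = 0.283 SD per SD of PCS.

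**3. True size of the listed model.** With independent errors assumed:
- The interaction slope is given variance 2/N; the true variance is 2(1−ρ)/N. Size = 2[1 − Φ(1.96/√(1−ρ))], and the same for Condition.
- The PCS slope is given variance 1/(2N); the true variance is (1+ρ)/(2N). Size = 2[1 − Φ(1.96/√(1+ρ))].

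| ρ | Condition and Condition-by-PCS | PCS |
|---|---|---|
| 0.3 | 1.9% | 8.6% |
| 0.5 | 0.56% | 11.0% |
| 0.7 | 0.03% | 13.3% |

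Simulation at ρ = 0.5 gives about 0.5% to 0.8% for the interaction and about 10.7% for PCS, at both N = 100 and N = 50. The paired analysis holds 5%.

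**4. Power for the interaction at b = 0.283, ρ = 0.5.**

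| N | Listed model (simulated) | Paired | Slope for 80% power, paired |
|---|---|---|---|
| 100 | about 0.51 | 0.80 | 0.283 |
| 50 | about 0.22 | 0.50 | 0.404 |

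**5. A participant class effect alone.** This gives the correct interaction test in completers (p = 0.192 by this route and by the paired regression in one simulated data set). But PCS is constant within a person: with 100 participants the design has rank 102 for 103 columns, so the PCS main effect cannot be estimated without its own between-participant error term.

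**6. Pooled, Group terms left out, no true moderation.** Let δ be the group difference in withdrawal effect and g the PCS gap in within-group SDs. In the paired model the variance falsely explained is E = (δg/4)²/(1+g²/4), the residual is R = 2(1−ρ) + δ²/4 − E, and λ = N·E/R. The Group-by-Condition effect for f2 = 0.02 satisfies N·δ²/4 = 8 at ρ = 0.5, so δ = 0.566. For g = 1.0: E = 0.0160, R = 1.064, λ = 1.51, false-positive rate 23%. For g = 0.5: λ = 0.44, rate 10%. With δ = 0.283 the rates are 6% to 9%. In the model as listed they are only about 2% to 6% and 1% to 2%, because its over-strict interaction test hides most of the confounding. With Group terms they return to 5%. The gaps are assumptions.

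**7. Power cost of Group terms.** λ falls to 8/(1+g²/4). For g = 0.5, 0.8, 1.0, 1.2, λ = 7.53, 6.90, 6.40, 5.88 and power = 0.78, 0.74, 0.71, 0.67, against 0.80. Simulation with PCS drawn at random gives 0.76, 0.72, 0.69, 0.67 against 0.79. If g is measured in overall PCS SDs, λ = 8(1−g²/4) and power is 0.77, 0.73, 0.68, 0.61.

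**The case against.** The plan never says the rows are independent. PROC GLM with a REPEATED statement, taking the two k values as responses and PCS as predictor, would give exactly the three listed effects with proper error terms. Regressing the within-person difference on PCS could also be called linear regression. Section 14.3 already declares Condition repeated, and Section 14 promises a detailed SAP. All of this is true, and it makes the defect an omission rather than a declared wrong model. It does not remove it: Section 14.4 names none of these routes, and its plain reading, together with Section 5.2, is ordinary regression.

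The population conflict is chiefly the synopsis against Section 3. Section 3.2 is compatible with Section 3, and Section 2.1 is general prose. That is fair, but the two main statements cannot both govern, and Section 14.4 does not choose.

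The 10% to 23% false-positive rates need pooling, a repaired error term and missing Group terms together, plus an assumed PCS gap. They are therefore a warning about a partial repair, not a property of the model as listed.

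The objective is secondary, no stated power is contradicted, and the deciding test errs on the strict side. That limits the severity, but a missed moderation effect remains a real cost.

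**Conclusion.** The concern holds and should be fixed. As listed, the test that decides Aim 2 runs at about 0.6% instead of 5%, and the PCS main effect at about 11%, at the plan's own correlation of 0.5. Over 0.3 to 0.7 the ranges are 1.9% to 0.03% and 8.6% to 13.3%. These sizes do not depend on any assumed effect. The power loss, from about 0.80 to 0.51 with 100 completers or 0.50 to 0.22 with 50, assumes a moderation slope of 0.283. The population contradiction is textual and needs no assumption; it moves the slope detectable with 80% power between 0.28 and 0.40 even when the error term is right. Confounding by Group applies only if the groups are pooled.

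**What to change.** In Section 14.4, replace the PROC GLM wording with the PROC MIXED repeated structure of Section 14.3, with Condition, PCS and Condition-by-PCS as fixed effects on log k (the transformation is already planned). In completers, GLM with an explicit REPEATED statement would serve equally well. Change Section 5.2 to match.

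State one Aim 2 population and reconcile the synopsis with Sections 2.1, 3, 3.2 and 14.4:
- **If both groups are pooled,** add Group and Group-by-Condition. The cost is about 2 to 13 points of moderation power for PCS gaps of 0.5 to 1.2 within-group SDs, and up to about 19 points if the gap is measured in overall SDs.
- **If PAIN only,** leave Group out. State that about 50 completers are available and that the slope detectable with 80% power is about 0.40 SD per SD of PCS.

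The change is wording only and needs no new data or software. It should be made before the data are examined, so that neither the population nor the error term is chosen afterwards.

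### If Aim 2 pools the PAIN and NO PAIN groups, the Condition-by-PCS test in 14.4 is confounded by Group x Condition, because the model has no Group terms

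*Combined protocol and SAP*

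**What the plan says.** Section 14.4 first examines Condition and PCS in separate PROC GLM models. It continues: "Then, a single GLM analysis will be conducted that includes Condition, PCS, and the" interaction of Condition with PCS. The decision rule is: "A significant interaction will indicate effect modification". No subject or repeated term is named, and neither Group nor Group x Condition appears. Both of these are in the primary PROC MIXED model in 14.3. The covariate rule in 14.2 covers only methadone dose, cigarettes, income, education and age, and only if they differ significantly between groups, so it cannot bring Group into the Aim 2 model.

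The documents disagree on whom Aim 2 covers:

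- Section 3 pools the groups and claims an independent role: "pain catastrophizing will independently modify the effect of precipitated opioid withdrawal on delay discounting", stated for both PAIN and NO PAIN.
- The synopsis, under secondary objectives, asks whether PCS "modifies the association between opioid withdrawal and delay discounting in the PAIN group".
- Section 3.2 ("Investigate the degree to which trait pain catastrophizing modifies the association between opioid withdrawal and delay discounting") and section 14.4 name no population.

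**The concern.** In the pooled analysis of section 3, PCS and Group are likely to be correlated: the groups are defined by chronic pain, and section 1.1 links catastrophizing to amplified pain processing and persistent pain. If the PAIN group also responds differently to withdrawal, a model that knows only PCS will credit part of that difference to PCS. The rule in 14.4 would then report effect modification, and section 3 would describe it as independent, even if PCS had no relation to the withdrawal response within either group.

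PCS modification is the only secondary objective listed in 3.2, and section 2.1 proposes later work on relapse that would build on such a finding. A chronic-pain difference reported as a catastrophizing effect would misdirect that work.

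**Working it through.** **Inputs from the documents.** Synopsis, rationale for number of subjects: N = 100 (50 per group), correlation of repeated measures 0.5, two-sided alpha 0.05, power above 80% for group, condition and interaction. Section 14.6: f² = 0.08 between groups and f² = 0.02 within subjects. No power figure is given for Condition-by-PCS.

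**Assumed.** The PAIN minus NO PAIN gap in PCS, written D, in within-group SD units. The documents give no value, so a range is shown.

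**Step 1: the plan's own power.** Noncentral F with 1 and 98 df and m = 2 measures:

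- Between groups: λ = f²·N·m/(1 + (m−1)ρ) = 0.08 × 100 × 2/1.5 = 10.67, power 89.9%.
- Within subjects, and the interaction if f² = 0.02 is applied to it: λ = f²·N·m/(1−ρ) = 0.02 × 100 × 2/0.5 = 8.0, power 79.97%, in line with the stated 80%.

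**Step 2: the interaction in SD units.** With ρ = 0.5 and unit variance, the withdrawal-minus-control change has variance 2(1 − 0.5) = 1. A group difference Δ in that change has λ = Δ² × 50/2. Setting λ = 8 gives Δ = √(8/25) = 0.566, or 0.57 SD.

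**Step 3: the bias.** Let change = Δ·Group + error and PCS = D·Group + error, with unit-variance errors, equal groups and no PCS effect within groups. The pooled slope of change on PCS, which is the Condition-by-PCS coefficient, is

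slope = (Δ·D/4)/(1 + D²/4).

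The true within-group slope is zero. With Δ = 0.566 the pooled slope is 0.0708/1.0625 = 0.067 at D = 0.5 and 0.1415/1.25 = 0.113 at D = 1.0. It is zero if either Δ or D is zero. Because PCS takes the same value in both sessions, the least-squares coefficient is the same with or without a subject term.

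**Step 4: rejection rates.** Simulated at 50 per group, Δ = 0.57 SD, no PCS effect within groups, nominal 5%. The subject-level test regresses the change score on PCS. Literal GLM treats the two sessions as unrelated observations.

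| Assumed PCS gap D | Subject-level, no Group terms | Subject-level, Group terms added | Literal GLM, no Group terms |
|---|---|---|---|
| 0.5 SD | 10% | 5% | 2% |
| 0.8 SD | 17% | 5% | 4% |
| 1.0 SD | 23% | 5% | 6% |
| 1.2 SD | 29% | 5% | 9% |

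Simulation error is about half a percentage point or less. Literal GLM with Group terms rejects about 0.5% of the time. With Δ = 0.3 SD the subject-level rates over the same gaps run from 6% to 12%. With Δ = 0 and D = 0.8 the subject-level rate is 4.8%.

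**Step 5: cost of adjustment.** Adding Group inflates the variance of the PCS coefficient by 1 + D²/4. If Condition-by-PCS itself has λ = 8, power falls from 80.0% to 77.5% at D = 0.5 (λ = 8/1.0625), 73.9% at D = 0.8 (8/1.16) and 70.7% at D = 1.0 (8/1.25).

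**Step 6: PAIN only.** Group is constant, so the bias cannot occur. With 50 subjects and f² = 0.02, λ = 0.02 × 50 × 2/0.5 = 4 and power is about 50%.

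**The case against.** **The population is unsettled.** The synopsis limits the objective to PAIN. If that governs, there is no confounding and Group cannot be fitted. This stands, and it makes the point conditional on pooling.

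**The rates are not those of the model as written.** Section 14.4 names PROC GLM without a subject term. Run that way, the test is conservative and exceeds 5% only at the larger assumed gaps. This stands for the rejection rates. It does not rescue the estimate, whose bias is the same, and correcting the error term alone would expose the full inflation.

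**A Group x Condition effect is not predicted.** A reader might take section 3, "with the greatest discounting observed in the PAIN group while in withdrawal", as forecasting the interaction that drives the bias. It does not: section 3 also expects PAIN to exceed NO PAIN in both sessions and withdrawal to exceed control in both groups, so two additive effects would give the same pattern, and under additivity nothing leaks. What remains is that 14.3 examines the interaction and the synopsis claims power for it, so the plan treats it as possible.

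**The PCS gap is assumed.** The only PCS difference that the plan predicts is by sex (14.4). This stands: the table shows a range, and 29% needs both a 1.2 SD gap and a full-size interaction.

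**Marginal modification is a legitimate target.** The objectives and the 14.4 rule speak only of modification, and 14.4 elsewhere uses the word independently to mean separate models. If only marginal modification is meant, the unadjusted term answers the question and rejection is not a false positive. But section 3 says PCS will "independently modify the effect of precipitated opioid withdrawal on delay discounting", which reads most naturally as over and above pain group.

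**Conclusion.** The point holds for a pooled Aim 2 analysis. The 14.4 model cannot separate modification by PCS from modification by chronic-pain group, so it does not support the independent effect claimed in section 3. At the planned interaction size, a subject-level test has a false-positive rate of about 10% to 29% over PCS gaps of 0.5 to 1.2 SD. Those figures rest on three conditions: both groups in the model, a real Group x Condition difference of 0.57 SD, and an assumed PCS gap. Without the interaction or without the gap there is no inflation.

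Two stronger readings are not supported. One is that Aim 2 as written will have an inflated error rate: the synopsis allows a PAIN-only analysis, and the literal GLM test is conservative. The other is that the exploratory models for somatization, depression and anxiety share the defect: 14.4 only explores those associations and claims no independence for them.

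This should be fixed, but it does not threaten the trial. It concerns a secondary aim, the primary model already carries Group x Condition, and section 14 promises a detailed SAP in which the change can be made.

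**What to change.** First reconcile the Aim 2 population across the synopsis, section 3, section 3.2 and section 14.4.

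- **If pooled:** fit Condition, PCS, Condition-by-PCS, Group and Group x Condition, with Condition as a within-subject repeated effect as in 14.3. Base any statement of independent modification on Condition-by-PCS from that model, and show the unadjusted estimate beside it.
- **If PAIN only:** say so in sections 3, 3.2 and 14.4 and remove the reference to both groups from the section 3 hypothesis. The Group terms are then not needed, but the repeated structure still is. State the power for 50 subjects, which is about 50% at f² = 0.02.

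The cost is wording and, if pooled, two model terms on data already being collected. The statistical price in the pooled case is the loss of power for Condition-by-PCS in step 5, from 80% to 77.5% at a 0.5 SD gap and about 71% at 1.0 SD.
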